Prospective 1:1 block randomized study, with random block sizes. Two arms: experimental and active control (Fig 1).

B. Sample

Individuals with breast cancer-related neuropathy will be recruited for this study using the following inclusion and exclusion criteria.

Inclusion criteria:

- Breast cancer survivors \geq 40 years old
- Symptomatic for neuropathy (CIPN20 sensorimotor score < 95 on transformed scale (100 maximum));
- postural control outside 70% CI for adults who are middle-aged without neurotrauma [20]);
- having completed taxane-based chemotherapy treatment at least 3 months ago;
- able to understand and comply with directions associated with testing and study treatments.

Exclusion criteria:

- Pre-existing vestibular deficit;

[figure not shown]

Fig1: Study design flowchart. TP = Testing timepoint.

- poorly controlled diabetes (hgA1C \geq 8);
- non-ambulatory or lower extremity amputation (assistive devices allowed);
- use of cytotoxic therapy during study (immune- and endocrine therapy allowed);
- participation in physical therapy during the study;
- contraindication to participate in Tango due to orthopedic issue (e.g., herniated vertebral disc);

In addition, survivors who are screened and found eligible to participate in this RCT will be asked to invite a companion to enroll with them in the study arm that the survivor is randomized into. (n=up to 100 companions)

Finally, up to 100 survivors screened who do not meet the criteria above will be offered enrollment without compensation in the intervention of their choice, along with their companion (up to n=100), as we have capacity to include them and using the “companion” consent form. Capacity will be defined based on space and staffing availability.

Therefore, in total, up to 200 survivors and up to 200 companions will be enrolled in Phase 2 of this protocol.

C. Measurement/Instrumentation

Data collected at baseline x 4, mid-intervention and post intervention (*collected at baseline x1 only):

- Adverse events (i.e., PRO-CTCAE[26], falls or loss of balance, illness or hospitalization since last visit)
- SF-36[25]
- EORTC QLQ-C30[15]
- Neuropathy symptoms: measured using original or modified forms of the EORTC CIPN-20[16]
- Sports Concussion Assessment Test (SCAT) Symptom inventory (for comparison to CIPN-20)[27,28]
- Pain: measured using original or modified forms of the Brief Pain Inventory (BPI)[29]

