- Fatigue: measured using original or modified forms of Cancer Related Fatigue (CRF) scales
- Rating of Perceived Exertion (RPE)
- Quantified measures via portable force plate: medial-lateral sway area, range, mean and variability during bilateral static standing with eyes closed[20]
- Timed-Up-and-Go (TUG)[30,31]
- Quantitative gait stability measures via portable motion capture system: average and variability measures of spatiotemporal gait parameters (e.g., stride length, stride time, step width)[22]*
- Mini-BEST[32]*
- Grip strength[33]*
- Goal Attainment Scale (GAS)[34]*
- Activities of Daily Living (ADL) [35] (e.g., Lawton-Brody iADL, Functional Status Questionnaire (FSQ) ADL, Katz ADL, QuickDASH[36])*
- Functional Fitness of Older Adults test [37]*
- Non-invasive Electroencephalography (EEG)*

Data collected within-session (before and after each session unless otherwise noted):

- Adverse events (before every session)
- Neuropathy: measured using original or modified forms of the EORTC CIPN-20[16]

- Sports Concussion Assessment Test (SCAT) Symptom inventory (for comparison to CIPN-20)[27,28]
- Pain: measured using original or modified forms of the Brief Pain Inventory (BPI)[29]
- Fatigue: measured using original or modified forms of Cancer Related Fatigue (CRF) scales
- Rating of Perceived Exertion (RPE)
- Quantified measures via portable force plate: medial-lateral sway area, range, mean and variability during bilateral static standing with eyes closed[20]
- satisfaction with intervention via 7-pt Likert Scale (after every session)[38]
- Goal Attainment Scale (GAS)[34] (before session, no more than once a week)
- Intrinsic Motivation Inventory (IMI)[39] (after session, no more than once a week)

Data collected by participant at home, daily, and reported to research staff on weekly basis:

We will ask participants to track the adverse event of falls or loss of balance using a daily journal that they take home with them or secure electronic data capture interface (e.g., REDCap, MyCap). We will collect these data weekly during the intervention, and for 6 months following the completion of intervention, through weekly check-ins with all participants

D. Detailed Study Procedures

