Aim1: We will evaluate change in postural control over 16 sessions of Tango (exp) vs HEX (control) (n=26 per group; 1:1 randomization) as primary endpoint. As secondary measures, we will assess: balance function (i.e., TUG) and PROs (i.e., symptoms, pain, fatigue, mood, quality of life) *monthly* including 1 month post-intervention completion; postural control and symptoms *within-session*; and falls incidence *weekly for 6 months following intervention completion*. **Hypothesis:** At primary endpoint, members of the exp group will show more improvement than members of the control group in measures sensitive to neuropathy disease state (i.e., sway variability and area).

a. Primary measure: Posture (RMSml): has shown clinically relevant for future fall prediction[40–43] and neuropathy detection in cancer[44–46] and diabetes[47,48] in a host of studies. As our primary measure we will calculate this measure of medial-lateral sway variability (RMSml). Postural control (30 s duration) will be collected 2x/week during multiple baseline testing, monthly thereafter for HEX, and before and after each session for the Tango group. Center of pressure (COP) data will be recorded (1000 Hz) as participants stand quietly on a level, static balance platform (Bertec Corp, Columbus, OH) with eyes closed (QEC). As in past work[20,38,44–46], we will collect 30 second (s) of COP data and interpret these data with regard to healthy within-subject variability as defined in a middle-aged cohort [20].

RMSml will be calculated (as described by Prieto[49]) as the root-mean-squared value of COP excursion in the medial-lateral direction (mm), a formula which effectively returns the standard deviation from the mean. All data will be captured using custom software written in LabView (National Instruments, Austin, TX, US). Our team ([name], [name]) has pioneered the biomechanical assessment of balance deficits associated with cancer treatment and neurorehabilitation [20,38,44–46]. Using center-of-pressure (COP) measures captured with portable force platform equipment, we have quantified the balance dysfunction that accumulates with cancer treatment sessions (Fig 1) [1,46,50] and identified a potential effect of Tango to remediate these effects[38]. Finally, in order to translate this quantified measurement paradigm to clinical care of individuals, we published normative measures of within-subject variability (WSV) [20] to enhance our interpretation of treatment effects.

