b. Secondary measures: Posture (other): will be calculated from the 30s duration of quiet standing data including COP ellipse area, velocity, and sample entropy[38]. In particular, the non-linear measure of sample entropy[38,51–54] may provide additional information regarding complexity of postural control regulation among cancer survivors with neuropathy. **Balance:** is a critical measure of clinical impact. The Timed Up-and-Go test, or **TUG**, (<2 min to administer) is a timed test of a person's ability to stand from a chair, walk 10 feet, turn around, and return to sitting with shorter times indicating better functional

balance. While our data indicate some clinical tests are not sensitive to chemotherapy-induced neuropathy state (e.g., Berg), Wampler et al (2007); Marshall et al. (2017); and Evans et al. (2019) reported that TUG time distinguished cancer survivors with neuropathy (n=20, 8, & 20 survivors respectively) from age-matched controls. **Patient-reported outcomes (PROs):** are critical secondary measures that will help us to understand participant perception of change with intervention. These will be collected 2x/week during multiple baseline testing then monthly thereafter with a subset captured per session to evaluate within-session effects. We will administer PROs during multiple baseline and monthly testing through retention. CIPN-20 and BPI instruments will be administered to complement one another: the CIPN 20 focuses on the effect of neuropathy symptoms on functional capacity while the BPI assesses pain symptoms. We will also collect the symptom inventory from the Sports Concussion Assessment Tool (SCAT). Additionally, we will document cancer-related fatigue (CRF), quality of life (SF-36), satisfaction with intervention, likelihood of recommending the intervention to a friend with neuropathy (this will be included as a question on the satisfaction with intervention survey), perceived benefit, intrinsic motivation, depression/apathy/ anxiety (PRO-CTCAE), and adverse events including falls. **Falls:** each participant will use a diary format to report daily changes in falls, symptoms, use of assistive devices, and amount of concurrent medication use during the study period. These factors will also be recorded by research staff within adverse event reporting 2x per week before Tango lessons. For 6 months after intervention completion, we will collect falls incidence weekly from participant daily dairy records.

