Feedback is used to improve future sessions. Monthly, we prompt participants to rate the likelihood of future engagement. **The Intrinsic Motivation Inventory (IMI)** was developed from the perspective of Self Determination Theory to assess 7 dimensions of experience: Interest/Enjoyment, Perceived Competence, Effort/Importance, Pressure/Tension, and Choice[39,57–61]. We administer the 9 item short form of the IMI weekly to optimize instruction around high Perceived Competence and low Pressure/Tension[58,59] as well as explore relationships between adherence, motor effects, and IMI dimensions (including perceived benefit (Effort/Importance)). The Patient-Reported Outcome version of the **Common Terminology Criteria for Adverse Events v5 (PRO-CTCAE):** developed by NCI, is standard protocol in oncology to screen for signs of depression, anxiety, and apathy associated with cancer treatment or progression[62]. While not an outcome measure, we collect this staff-administered assessment per visit for adverse event screening, using the data to monitor and compare descriptive

statistics between groups. Changes in depression, anxiety, or apathy identified within check-ins, will be addressed.

c. *Within-Session Effects* Posture: will be captured before and after each Tango session in order to assess within-session change over time. A subset of **PROs**: (i.e., CIPN-20, BPI, and CRF) will be collected routinely before and after Tango training to allow analysis of within-session change. Finally, satisfaction with intervention will be collected after each session

Aim2: We will evaluate change in gait variability after 16 sessions of Tango (exp) vs HEX (control) (n=26 per group; 1:1 randomization). As secondary measures, we will analyze local and orbital dynamic stability (pre, post, and 1mo post-intervention), PROs (monthly), and falls incidence (weekly) following intervention completion. **Hypothesis:** At primary endpoint, members of the exp group will improve more relative to control group members in gait variability (i.e., stride-to-stride variability in speed).

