For **Aim 1**, a linear mixed effects model will be used to model postural sway (RMSml). Fixed effects will be included for time, treatment, treatment-by-time interactions, and concurrent medication use. Random effects for subjects will be used to account for correlation between observations from the same subject. The primary estimand will be a difference-in-difference representing the difference in mean RMSml change from baseline to week 16 between treatment groups. While we expect balance between the two groups due to randomization, we will adjust for potential confounders including baseline RMSml, age, body mass index, concurrent medications (e.g., duloxetine) and other variables if imbalance between groups occurs by chance. Similar analyses will be performed for the PROs sensory symptoms (CIPN-20), pain (BPI-SF), fatigue (0–10 Likert), quality of life (SF-36), and falls incidence following intervention completion. Finally, Pearson's R will be calculated to correlate postural control and balance outcomes, PROs, and future falls incidence.

For **Aim 2**, a similar analysis strategy will be used to compare biomechanical mobility between the two groups (linear mixed models; one-sided hypothesis test) as well as the correlation between biomechanical mobility outcomes, PROs, and falls incidence following intervention completion (Pearson's R).

Not all enrolled subjects will complete the intervention and have follow-up data. The linear mixed model analyses can use available data from all participants with at least one observation, regardless of whether or not they complete follow-up. We will compare the baseline characteristics of subjects who complete the study to those who drop out to assess the potential for attrition bias. A sensitivity analysis will be performed using multiple imputation to assess the impact drop-out has on study conclusions.

V. Funding

This project was funded, initially in Phase 1, through a 2015-16 Pelotonia Undergraduate Fellowship. We secured Phase 2 funding in 1R21AG068831 through the NIH National Institute of Aging (Note: this includes visit reimbursement for cancer survivors only).

VI. References

- [1] S.M. Monfort, X. Pan, R. Patrick, J. Singaravelu, C.L. Loprinzi, M.B. [name], A.M.W. Chaudhari, Natural history of postural instability in breast cancer patients treated with taxane-based chemotherapy: A pilot study, *Gait and Posture*. (2016). <https://doi.org/10.1016/j.gaitpost.2016.06.011>.

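### During the intervention, staff ask about adverse events and medication far more often in Tango than in HEX, and the plan does not limit between-group summaries to sources common to both arms.

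*Combined protocol and SAP*

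**What the plan says.** All references are to the combined protocol and SAP, part IV (Phase II).

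- **Testing visits, both arms** (IV.C Measurement/Instrumentation). At baseline, mid-intervention and post-intervention the list includes "Adverse events (i.e., PRO-CTCAE[26], falls or loss of balance, illness or hospitalization since last visit".
- **Sessions** (IV.C, within-session list). The entry is "Adverse events (before every session", with no arm named.
- **Weekly contact, both arms** (IV.C, data collected at home). On falls and loss of balance: "We will collect these data weekly during the intervention, and for 6 months following the completion of intervention, through weekly check-ins with all participants".
- **Diary, both arms** (IV.D, Aim 1, secondary measures, Falls): "each participant will use a diary format to report daily changes in falls, symptoms, use of assistive devices, and amount of concurrent medication use".
- **Extra staff recording** (same paragraph, of the diary items): "These factors will also be recorded by research staff within adverse event reporting 2x per week before Tango lessons".
- **PRO-CTCAE** (IV.D, Aim 1, secondary measures): "we collect this staff-administered assessment per visit for adverse event screening". The text says it is not an outcome measure, but that its data will be used for monitoring and compared descriptively between the groups.
- **Visit frequency by arm** (IV.D, Aim 1, primary measure, stated for posture): "monthly thereafter for HEX, and before and after each session for the Tango group".
- **Medication in the model** (IV.F, Statistical Analysis Plan, Aim 1): "Fixed effects will be included for time, treatment, treatment-by-time interactions, and concurrent medication use". Neither the data source nor the time point for medication use is given.

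**The concern.** The pre-lesson recording comes on top of the diary and is written for Tango only. The adverse-event item includes PRO-CTCAE, falls, illness and hospitalization, so a Tango attender is asked about all of these by staff before each of 16 lessons. For everything except falls and loss of balance, the only staff contacts written explicitly for HEX during the intervention are the shared testing visits.

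More frequent asking, over a shorter recall period, usually finds more events. A by-arm table built from all records would then mix a difference in how often people were asked with any difference in what happened to them. Tango could look less safe than it is, or HEX could look falsely reassuring. Calling the comparison descriptive does not prevent this, because a table by randomised arm will be read as comparative safety data. Medication use is exposed to the same asymmetry, and it also enters the primary model.

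**Working it through.** The plan gives no figure for event capture, so there is nothing of its own to reproduce here. The sample size does not depend on this point.

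**Step 1. Length of the intervention.** There are 16 sessions (IV.D, Aim 1) and lessons are twice a week (IV.D, Falls), so 16 / 2 = 8 weeks. The SAP places the primary contrast at week 16. The two need reconciling, so both readings are shown.

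**Step 2. Staff asks during the intervention, full attendance.** Monthly visits are about 2 over 8 weeks (mid and post) or about 4 over 16 weeks.

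| Item | Period | Tango | HEX |
|---|---|---|---|
| Non-fall adverse events, check-ins not counted | 8 weeks | 16 + 2 = 18 | 2 |
| Same | 16 weeks | 16 + 4 = 20 | 4 |
| Falls, check-ins counted in both arms | 8 weeks | 16 + 8 + 2 = 26 | 8 + 2 = 10 |
| Same | 16 weeks | 16 + 16 + 4 = 36 | 16 + 4 = 20 |

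For falls, leaving out the shared visits, the ratio of contacts is (16 + 8) / 8 = 3 to 1, or (16 + 16) / 16 = 2 to 1.

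The non-fall rows take IV.C literally, where the weekly check-in covers only falls and loss of balance. The PRO-CTCAE text mentions mood changes found at check-ins, which hints at wider content but does not define it. If the check-ins cover all adverse events, the falls rows apply to those events too.

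**Step 3. Non-fall adverse events, true ratio 1.** Recorded ratio = capture in Tango / capture in HEX. Capture rates are assumptions; the documents give none.

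- 0.9 / 0.8 = 1.13
- 0.9 / 0.6 = 1.5
- 0.9 / 0.45 = 2.0

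**Step 4. Falls during the intervention, true ratio 1.** Let s be capture by the channels common to both arms, and q the chance that the extra Tango ask picks up a missed event. Recorded ratio = [1 − (1 − s)(1 − q)] / s. Both inputs are assumptions, and the formula treats the extra ask as independent of the common channels.

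| s | q = 0.3 | q = 0.5 | q = 0.7 |
|---|---|---|---|
| 0.60 | 0.72 / 0.60 = 1.20 | 0.80 / 0.60 = 1.33 | 0.88 / 0.60 = 1.47 |
| 0.80 | 1.08 | 1.13 | 1.18 |
| 0.90 | 1.03 | 1.06 | 1.08 |
| 0.95 | 1.02 | 1.03 | 1.04 |

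**Step 5. Which planned analyses are reached.**

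- *Descriptive PRO-CTCAE comparison:* reached, because the data are collected per visit and visits differ by arm.
- *On-intervention adverse events by arm:* reached if such a table is made from all records.
- *Falls in the SAP:* not reached. The modelled outcome covers the period after the intervention, when lessons have ended and both arms follow the same weekly schedule. The extra channel is absent, so with equal capture the ratio is 1.00.
- *Medication covariate:* the source is not stated, so it may or may not draw on the pre-lesson records.

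**The case against.** The strongest reply is that HEX is well covered. Every participant keeps a daily diary of falls, symptoms, device use and medication, has a weekly check-in, and attends the same testing visits. This stands against one tempting reading, that HEX has no comparable contact: the difference is in frequency and content, and for falls it is about 2 or 3 to 1. It does not settle the matter for PRO-CTCAE, illness and hospitalization, because the check-in is tied explicitly only to falls and loss of balance.

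A second reply is that no on-intervention falls comparison is planned. That is correct. A reader might infer that the planned falls analysis is biased, but it covers the post-intervention period, with equal contact in both arms. The falls ratios in step 4 would apply only to a by-arm table that the SAP does not specify, and they shrink to about 1.02 to 1.08 if common capture is 90% to 95%. They would be smaller still if people who omit a fall from the diary also omit it before a lesson.

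A third reply is that the comparison sentence covers only PRO-CTCAE, which is not an outcome, and does not say that counts are compared. Scores averaged per visit, or compared at shared visits, would not rise automatically with more Tango visits. This also stands, but the plan does not choose such a summary. Counts, worst grades and the proportion ever reporting a symptom all tend to rise with the number of asks.

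Finally, the within-session list names no arm. The neighbouring text on posture, falls and within-session effects ties those sessions to Tango.

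**Conclusion.** The concern holds for on-intervention adverse events. Followed as written, the plan adds 16 staff asks in Tango that HEX does not have, then compares per-visit PRO-CTCAE data between the groups without limiting the comparison to shared sources. The likely direction is over-recording in Tango relative to HEX, which counts against the experimental arm on safety and does not favour it.

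The size is unknown. The ratios of 1.13 to 2.0 for non-fall events rest wholly on assumed capture rates, and the contact counts assume full attendance and a check-in limited to falls and loss of balance.

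A reader might infer that the primary RMSml result is biased through the medication covariate. The documents do not support this. Every participant's diary records medication, the SAP does not say that pre-lesson records feed the model, and no direction or size of effect on the estimate has been shown. What can be said is that the source is unspecified while capture differs by arm. This is a limited weakness with a cheap remedy, and it leaves the efficacy analyses as they are.

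**What to change.** 1. Ask the same adverse-event and medication questions in both arms at the weekly check-in already planned for everyone, and state its content in IV.C.
2. State in IV.F that between-group adverse-event and PRO-CTCAE summaries, and the medication covariate, use only sources common to both arms: the diary, the weekly check-in and the shared testing visits.
3. Log the source of each record.
4. Keep the pre-lesson recording for monitoring, and list events captured solely by that route separately.
5. Reconcile 16 sessions at two a week with the SAP's week 16, so that the observation period is the same in every table.

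The cost is a few questions at an existing contact and some SAP wording; the sample size does not change. Tango-only reports leave the comparative table but are still reported. One limit remains: frequent questioning may prompt Tango participants to keep fuller diaries. Common sources therefore equalise scheduled contact but cannot guarantee equal capture.

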a. *Instrumented measures:* Using a commercially available inertial measurement unit (IMU) and electromyographic (EMG) system (Delsys Trigno, Boston MA), we will record kinematics & muscle activity during performance of the MiniBEST and 3 minutes of steady-state walking. The **Mini Balance Evaluation System Test (MiniBEST)**: evaluates sensory organization, anticipatory and reactive postural control, and dynamic gait indices[63]; was recently recommended for use in studies of neuropathy[13]; and discriminated BC survivors from controls in at least 1 prior study[32]. Instrumentation of MiniBEST will enable calculation of spatiotemporal, kinematic, and co-contraction measures. **Gait variability:** is indicative of mild cognitive impairment [64], age [65], fall risk in the elderly [22,66,67], and neuropathy [68] regardless of age or type of cancer[69] including specifically in BC[70,71]. These data add to findings from MPI [name] that orbital stability during gait worsens with even mild neuropathy when compared to age-matched controls[72]. Therefore, gait variability is a relevant behavioral mechanism to study[22,66,67]. Our preliminary data suggests gait variability is trainable among cancer survivors through Tango practice [73]; if feasible to study, gait variability/stability may provide critical insight into neuromotor mechanisms relevant for treatment of persons with neurotrauma. Participants will walk overground at their own speed for a minimum of 3 minutes after a 30 second acclimatization period. gait characteristics will be calculated per stride (e.g., speed). From multiple strides collected over 3 minutes, the coefficient of variation (CV) will be calculated for step length, gait speed and other measures of variability previously found sensitive to health status [22,66,73]. **Local dynamic stability[74,75] and orbital stability[72,76]:** will also be analyzed, measures shown sensitive to neuropathy that have yet to be employed in prospective interventional studies. **Co-contraction index (CCI):** calculated from electromyographic (EMG) signals of the tibialis anterior and medial gastrocnemius muscles, provides unique insight into neuropathy effects[68,77]. CCI will be calculated during steady-state gait[68] and quiet standing tasks[77] within the MiniBEST. If proven feasible, the ability to assess CCI in concert with biomechanical measures of balance (i.e., postural control) and locomotion (i.e., gait variability, orbital stability, and local stability) will represent a powerful methodological combination through which to investigate mechanisms of neurorecovery in future trials. MPI [name] has extensive experience distilling biomechanical variables of interest into clinically-relevant performance measures of neurologic health [1,44,78–80,80–87] for her own research as well as for other leading investigators. **PROs, AEs, and future falls incidence:** as above.

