
Data collection: data may be collected using paper or electronic (e.g. MyCAP) versions of approved instruments.

Data storage: paper versions of source documentation will be kept in a locked cabinet within an OSU office that is accessible only to OSU clinical or research staff. Electronic data may be stored in a password protected spreadsheet or through RedCAP.

Interventions: training may be delivered in-person, via video conferencing, or via asynchronous instruction.

E. Internal Validity

All measures will be conducted by a researcher trained in the administration of the measure.

F. Data Analysis

Sample Size Justification: Preliminary data from our group was used to determine sample size requirements for this proposed randomized trial. **Aim 1:** Five cancer survivors with postural control deficits (RMSml>4.0mm) at baseline who participated in Tango practice improved RMSml from mean(SD) of 7.9(1.2) at baseline to 4.6(0.5) after 8 Tango sessions. Assuming more heterogeneity in our analysis sample, (SD=2.7 in control and intervention groups) we estimate Cohen's $d=1.22$. Thus we require an analysis sample of $n=14$ participants per group to provide 85% power at a 5% type I error rate. To account for anticipated drop-out and Aim2 analysis we will **enroll n=26 participants per group.** **Aim 2:** Preliminary data shows an Coefficient of Variation gait speed (CVspeed) SD of approximately 1.2 among survivors with neuropathy and postural deficits prior to Tango practice. With a sample size of $n=19$ per group (per Aim1) and this SD, we have 80% power to detect a difference of 1.32 ($d=1.1$). A cohort of 7 survivors with heterogeneous treatment progress (during and after chemotherapy exposure), not screened for or limited to those with postural control deficits, demonstrated a decrease in CVspeed ($p=0.003$) from 3.0(1.15) to 2.2(1.10) after ≤ 16 sessions of Tango practice ($d=0.711$). We will enroll **n=26 participants per group** to detect a reduction of this magnitude with 80% power.

Statistical Analysis Plan: Unless otherwise noted, all analyses will be performed on an intent-to-treat basis, and all hypothesis tests will be two-sided and at the 5% significance level. Enrolled participant characteristics will be summarized by assigned treatment groups.

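### Outcome assessment in Phase 2 is protected only by tester training: gait, stability, co-contraction and sample-entropy processing, and TUG timing, can be done by staff who know the arm

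*Combined protocol and SAP*

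**What the plan says.** Section IV.A describes the design: "Prospective 1:1 block randomized study, with random block sizes. Two arms: experimental and active control". Section IV.E, Internal Validity, is a single sentence: "All measures will be conducted by a researcher trained in the administration of the measure". It repeats the Phase 1 sentence in III.E. No section of the document says that testers, data processors or the analyst are masked, or that testers are separate from session staff.

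Section IV.D, Aim 1 a, sets the post-baseline sway schedule as "monthly thereafter for HEX, and before and after each session for the Tango group". Aim 1 b adds that falls, symptoms, assistive devices and medication use are "recorded by research staff within adverse event reporting 2x per week before Tango lessons".

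The outcomes differ in how much judgement they leave:
- **RMSml** (primary, Aim 1 a) is computed by a cited formula from 30 s of eyes-closed force-plate data captured by software.
- **Sample entropy** (Aim 1 b, secondary) comes from the same recording. No computation settings are given.
- **TUG** (Aim 1 b, secondary) "is a timed test of a person's ability to stand from a chair", walk, turn and sit again. The plan does not say who times it or with what instructions.
- **Aim 2 measures** (Aim 2 a): the team will "record kinematics & muscle activity during performance of the MiniBEST and 3 minutes of steady-state walking", then derive coefficients of variation per stride, local and orbital stability, and a co-contraction index. No rule is given for which strides count, how artefacts are handled or when a trial is discarded.

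Section IV.F tests the Aim 2 comparison one-sided.

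**The concern.** Training makes testers consistent. It does not stop someone who knows the arm from encouraging one participant more than another, stopping the watch a little earlier, or rejecting an awkward walking segment. The plan's schedule creates that knowledge: Tango participants have sway tests around every class and HEX participants have them monthly. Nothing keeps the people who run those visits away from endpoint testing or file processing.

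At stake are the Aim 2 comparison and a functional secondary outcome. If Tango came out ahead on gait variability, stability or co-contraction, the trial could not show that stride selection or trial exclusion had played no part. Because Aim 2 is tested one-sided, any bias towards Tango pushes results into the only rejection region.

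**Working it through.** **1. Is there a masking provision anywhere?** IV.A gives randomisation with random block sizes and an active control. IV.F gives intent-to-treat analysis, a comparison of completers with drop-outs, and multiple imputation as a sensitivity analysis. These address allocation and attrition. None addresses who measures or processes outcomes, and IV.E speaks only of training.

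**2. Would staff know the arm?** The two statements in IV.D (sway tests before and after each Tango session but monthly for HEX; staff records taken before Tango lessons) mean that staff at those visits know it. The documents do not say whether the same people conduct the endpoint tests or process the files.

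**3. Where can that knowledge act?**

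| Outcome | At capture | At processing |
|---|---|---|
| RMSml | force plate; little room | fixed formula; little room |
| Sample entropy | force plate; little room | settings not fixed |
| Gait CV, local and orbital stability | IMU, 3 minutes or more of walking | stride selection, artefacts, exclusions not fixed |
| Co-contraction index | EMG | signal handling and exclusions not fixed |
| TUG | timed, tester unspecified | none |

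**4. The plan's own figures.** The plan gives no figure for assessment bias. Its Aim 2 sample size shows which test it appears to have in mind. For d = 0.711 at 80% power, a one-sided 5% two-sample t-test needs 25.2, rounded up to 26 per group, and 26 per group gives 81% power. This agrees with the stated 26 per group at 80% power. (For Aim 1, d = 3.3/2.7 = 1.22 at 85% power, two-sided, needs 13.1, rounded up to the stated 14.)

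**5. Illustration of consequence.** Assumptions: no true effect, a two-sample t-test, and a systematic bias of b SD towards Tango. The documents supply no b, so a range is shown. The test statistic is then noncentral t with df = 2n − 2 and noncentrality b × √(n/2). For n = 26, √13 = 3.606, df = 50 and the one-sided critical value is 1.676:
- b = 0.1: noncentrality 0.361, rejection 9.9%
- b = 0.2: noncentrality 0.721, rejection 17.5%
- b = 0.3: noncentrality 1.082, rejection 28.2%

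| Analysed per group | Test | b = 0 | 0.1 | 0.2 | 0.3 |
|---|---|---|---|---|---|
| 26 | one-sided 5% (Aim 2) | 5% | 9.9% | 17.5% | 28.2% |
| 19 | one-sided 5% | 5% | 9.0% | 14.9% | 23.0% |
| 26 | two-sided 5% | 5% | 6.4% | 10.9% | 18.6% |

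The planned mixed model would give somewhat different values. The table shows scale only.

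**The case against.** The strongest reply is that most outcomes are instrumented, the primary one most of all, and that the gait protocol already limits discretion through a 30-second acclimatisation period, at least 3 minutes of walking, and CVs taken from the strides in that period. Processing may also be defined in the cited method papers. This stands for RMSml and narrows the point for gait. It does not remove it: the walking time is a minimum, artefact handling and trial exclusion are not mentioned, and the protocol does not adopt a cited paper's settings as fixed for this trial.

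Several stronger readings are tempting, and the documents do not support them:
- *Training is the trial's sole validity safeguard.* It is the sole one stated for outcome assessment. Randomisation, the active control, intent-to-treat analysis and the attrition checks are safeguards of other kinds.
- *PRO-CTCAE is a biased outcome because staff administer it.* IV.D says it is not an outcome measure; it is for adverse event screening and is compared only descriptively.
- *MiniBEST scores at follow-up are exposed.* No rater-scored total is named as an endpoint and no follow-up schedule is stated for it. IV.C marks Mini-BEST and gait with a footnote about baseline collection. Read literally, it would leave no post-intervention data, which conflicts with the Aim 2 comparisons after treatment and at 1 month.
- *A TUG difference will be tested and claimed.* TUG is named as secondary in IV.D, but IV.F does not list it among the similar between-group analyses.
- *The open-ended gait list ("other measures of variability previously found sensitive to health status") is a masking fault.* It is a selective-reporting matter, which masking testers would not cure. The Aim 2 hypothesis itself names speed variability.
- *A bias can be expressed as a share of d = 0.711.* That d is an uncontrolled before-after change in 7 survivors, so it is no yardstick for a between-arm bias.

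**Conclusion.** The point holds as a risk of bias, not as bias shown. For outcome assessment the plan requires training and nothing more, and its schedule makes knowledge of arm likely among session staff. The primary RMSml result is largely spared. The exposed outcomes are Aim 2 gait variability, local and orbital stability and co-contraction, sample entropy in Aim 1, and, at timing, TUG.

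The documents give no basis for sizing the bias. Under the stated assumptions (no true effect, 26 analysed per group, bias of 0.1 to 0.3 SD towards Tango), the nominal 5% one-sided error for Aim 2 would become about 10% to 28%. The conclusion does not depend on that range, but the range shows that even a modest bias would matter at this sample size. The change should be made before arm labels are joined to processed data, because masking cannot be restored afterwards.

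**What to change.** In IV.E, require that all COP, IMU and EMG files be stored under a code that carries no arm, and that processing settings, stride selection and bad-trial exclusions be fixed in writing and completed on the coded files before arm labels are merged. The cost is file coding and a processing lock. Sample size, endpoints and visits do not change, and this step is worth making alone.

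Where existing staffing allows, have post-baseline TUG timed, with a fixed instruction script, by a team member who neither leads nor attends that participant's sessions. This is conditional because the documents do not describe staffing; its cost is a scheduling constraint. In either case, IV.E should state who times TUG, who processes the files, and whether each is masked.

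Reconcile the baseline-collection footnote in IV.C with the post-intervention and 1-month comparisons in Aim 2, so that it is clear which follow-up files the processing rule covers.
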